#### 10.6.3 **Vital Signs**

Analyses will be performed for vital sign safety data collected at baseline and from first exposure to acalabrutinib to 30 days after last dose of acalabrutinib or up to the safety follow-up visit date, whichever is later. Summary statistics (mean, standard deviation, median, minimum and maximum) will be produced for vital signs at baseline, post-baseline values from the last visit, minimum and maximum post-baseline values, and changes of these post-baseline values from baseline. In addition, blood pressure is graded and the maximum post-baseline grade will be presented. Systolic Blood Pressure is graded by CTCAE as Grade 0 ( $\leq 119$  mm Hg), Grade 1 (120-139 mm Hg), Grade 2 (140 – 159 mm Hg), Grade 3 ( $\geq 160$  mm Hg). Diastolic Blood Pressure is grade as Grade 0 ( $\leq 79$  mm Hg), Grade 1 (80 -89 mm Hg), Grade 2 (90 – 99 mm Hg), Grade 3 ( $\geq 100$  mm Hg). In order to be included in the table, a subject must have at least one post-baseline value for the given time point.

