### 10.6.2 Laboratory Abnormality

All of the laboratory tests are performed in central laboratory and/or in local laboratory. Analyses will be performed for laboratory test data collected at baseline and from first exposure to acalabrutinib to 30 days after last dose of acalabrutinib or up to the safety follow-up visit date, whichever is later. Laboratory test for hematology, serum chemistry, and T/B/NK cell count up will be performed in central laboratory with reference range and the results will be reported in standard international units or conventional units when appropriate. Applicable laboratory test results will be graded according to CTCAE Version 4.03 or higher. AMA (American Medical Association (AMA) Manual of Style 10th Edition 2017) laboratory values will be applied whenever reference ranges are not available (e.g., local laboratory data).

For selected laboratory test parameters, summary statistics (mean, standard deviation, median, minimum and maximum) will be produced at baseline, post-baseline values from the last visit, minimum and maximum post-baseline values, and changes of these post-baseline values from baseline. Post-baseline toxicity grade greater than baseline grade will be presented in the treatment-emergent laboratory abnormality table. Shift from baseline to the worst grade from first exposure to acalabrutinib to 30 days after last dose of acalabrutinib or up to the safety follow-up visit date, whichever is later, will be provided as shift tables for selected parameters.

To be included in the summary table, a subject must have at least one post-baseline value for the given time point.

- *Lymphocytosis*

Lymphocytosis is defined as an elevation in absolute lymphocyte count (ALC) of  $\geq 50\%$  compared to baseline and a post-baseline assessment  $>5 \times 10^9/L$  (Wang 2013). The number of subjects with at least one occurrence of lymphocytosis will be summarized. For subjects with lymphocytosis, resolution of lymphocytosis is defined as 1) a decrease of ALC value to the baseline level or lower, or 2) a decrease of ALC value that is below  $5 \times 10^9/L$ , whichever occurs first. Duration of lymphocytosis (DOL) is defined as the duration of time from the earliest date on which the ALC value met the lymphocytosis criteria at a post-baseline assessment to the earliest date on which a subsequent ALC value met the resolution criteria.

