#### 10.6.4 **ECOG Performance Score**

Change of ECOG score from baseline to the worst score during the period from first exposure to acalabrutinib to 30 days after last dose of acalabrutinib or up to the safety follow-up visit date, whichever is later will be provided as shift tables.

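### The graded blood pressure table shows only the maximum post-baseline grade, so it cannot tell new or worsened elevation from elevation already present at baseline

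*SAP*

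**What the plan says.** SAP 10.6.3 has two layers.

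- **Ungraded values.** "Summary statistics (mean, standard deviation, median, minimum and maximum) will be produced for vital signs at baseline", for the last, minimum and maximum post-baseline values, "and changes of these post-baseline values from baseline".
- **Grades.** In addition, "blood pressure is graded and the maximum post-baseline grade will be presented". The bands are absolute levels. For systolic pressure the lowest raised band is "Grade 1 (120-139 mm Hg", followed by 140 to 159 for Grade 2 and 160 or more for Grade 3. Diastolic bands are built the same way. The only stated condition for entering the table is that "a subject must have at least one post-baseline value for the given time point".

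The sections on either side treat graded data differently. For laboratory tests, 10.6.2 states: "Post-baseline toxicity grade greater than baseline grade will be presented in the treatment-emergent laboratory abnormality table". It also plans, for selected parameters, "Shift from baseline to the worst grade from first exposure to acalabrutinib to 30 days after last dose of acalabrutinib". For performance status, 10.6.4 plans shift tables of "Change of ECOG score from baseline to the worst score during the period from first exposure to acalabrutinib".

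Hypertension is an event of clinical interest (10.6.1). Appendix 14.4 defines it by the narrow MedDRA hypertension query on reported adverse events, not by measured pressure.

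**The concern.** A grade based only on level says nothing about when the elevation began. Someone who enters at 150 mm Hg and stays there gets the same maximum Grade 2 as someone who rises from 115 to 150.

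Three features of this trial make the distinction matter. Safety is the primary objective. The cardiovascular exclusion (protocol 3.4.2, criterion 4) sets no blood pressure limit, so subjects with raised pressure can enroll. Both cohorts receive acalabrutinib, so no drug-free group shows how often a maximum of Grade 2 or 3 would occur anyway.

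Without the baseline grade, a reader of the study report cannot judge whether a given number of subjects at Grade 2 or 3 is a signal or a description of who was enrolled.

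**Working it through.** **1. The plan's own figure.** There is none on this point. The documents give no blood pressure values or expected rates.

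**2. What each planned output can answer.** The question is: of the subjects whose measured pressure reached Grade 2 or 3, how many had risen above their baseline grade?

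| Output | Based on | Compared with baseline? | Answers the question? |
|---|---|---|---|
| Maximum post-baseline grade (10.6.3) | Measured pressure | No | No |
| Numeric change from baseline (10.6.3) | Measured pressure | Yes, as mean, SD, median and range | No: group summaries do not count subjects who changed grade |
| Hypertension events (10.6, 10.6.1, 14.4) | Reported adverse events | Yes: onset or worsening on or after first dose | No: depends on an event being reported |
| Laboratory grades (10.6.2) | Laboratory tests | Yes | Not blood pressure |
| ECOG shift (10.6.4) | ECOG score | Yes | Not blood pressure |

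On the third row, protocol 6.1.1 says when a laboratory value becomes an adverse event but gives no corresponding rule for vital signs.

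**3. Possible size, on assumed inputs.** Each subject has a true systolic level drawn from a normal distribution. One baseline reading and k post-baseline readings each add independent normal visit-to-visit error, with no drug effect. Readings are graded with the SAP cut-points of 120, 140 and 160 mm Hg.

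Assumed values were mean 125, 130 or 135; between-subject SD 12 or 15; visit-to-visit SD 6 or 10; and k = 4, 6 or 17. That gives 3 × 2 × 2 × 3 = 36 settings, with 100,000 simulated subjects in each. Taking Cycle 1 Day 1 as baseline, the Appendix 5 schedule gives 4 later readings by the end of Cycle 1, 6 by the end of Cycle 2, and 17 through Cycle 12 plus the follow-up visit.

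| Mean / between SD / visit SD / k | Grade ≥2 at baseline | Maximum Grade ≥2 | Of those: Grade ≥2 at baseline | Of those: no worse than baseline |
|---|---|---|---|---|
| 125 / 12 / 10 / 17 | 17.8% | 60.1% | 28.2% | 19.0% |
| 130 / 15 / 10 / 6 | 30.0% | 57.7% | 48.4% | 34.1% |
| 135 / 15 / 6 / 4 | 38.8% | 54.0% | 68.1% | 56.4% |
| Range over all 36 settings | 14% to 40% | 25% to 85% | 28% to 68% | 19% to 56% |

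**4. One setting in a planned cohort of 20.** In the middle row, 20 × 0.577 = 11.5 subjects would show a maximum of Grade 2 or higher. They split as follows:

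- no worse than baseline: 11.5 × 0.341 = 3.9
- Grade 2 at baseline, rising to Grade 3: 11.5 × (0.484 − 0.341) = 1.6
- below Grade 2 at baseline: 11.5 × (1 − 0.484) = 5.9

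The planned table shows only the total. A shift table shows all three parts. The last two parts arise here with no drug effect, purely from taking the highest of several readings, and a shift table does not remove them.

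**The case against.** A reader might infer that the SAP counts hypertension present before the first dose as if it arose on treatment. The documents do not support that. The table is described as a maximum post-baseline grade and is never called treatment-emergent, a term that 10.6.2 uses for laboratory data when it is meant. Hypertension as an event of clinical interest is counted from treatment-emergent events, which by definition leave out unchanged pre-existing disease. Baseline values and changes from baseline, including the change to the maximum, are also planned.

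Other arguments lower the stakes:

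- The SAP has no universal shift-table rule; laboratory shifts are for selected parameters only.
- Protocol 5.5.1 asks only that vital signs be tabulated and summarized, and 10.6.3 exceeds that.
- The analysis is descriptive, SAP section 5 plans no formal tests, and no endpoint depends on the blood pressure grade.
- The simulated percentages rest wholly on assumptions. Part of the rise from baseline to maximum comes from repeated readings, which the remedy leaves in place.

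All of this stands, and it limits the point to what the graded table can show. It does not close the gap. None of the other planned outputs gives a count, from measured pressures, of subjects whose grade rose.

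**Conclusion.** The point holds as a modest reporting gap in the primary safety objective. As planned, the graded table cannot show whether a Grade 2 or 3 pressure is new, worsened or unchanged. That conclusion rests on the SAP text alone.

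The size is illustrative. Under the assumed no-effect inputs, 19% to 56% of subjects with a maximum of Grade 2 or higher are no worse than at baseline. The range is wide because mean pressure, both SDs and the number of readings are all unknown, and only systolic pressure was simulated. It is not a forecast for this trial. The stronger conclusion, that pre-existing hypertension is misreported as treatment-emergent, should not be drawn.

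**What to change.** In SAP 10.6.3, present the maximum post-baseline grade as a shift table of baseline grade by worst post-baseline grade, separately for systolic and diastolic pressure. Include a row for missing baseline, so that the column totals still give the maximum-grade distribution now planned. Use the same baseline reading as the numeric summaries. Beneath the table, report the number and percentage of subjects whose grade rose above baseline, which is the rule 10.6.2 already applies to laboratory grades.

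Keep the numeric summaries, including the change to the last visit. The last-visit change is not a worst-of-many reading, so it helps in judging how much of the shift comes from repeated measurement.

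The cost is a sentence or two of SAP wording and one reformatted table for each pressure. Vital signs are already scheduled at screening and at each visit (protocol Appendix 5), so no new data are needed.

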#### 10.6.4 **ECOG Performance Score**

Change of ECOG score from baseline to the worst score during the period from first exposure to acalabrutinib to 30 days after last dose of acalabrutinib or up to the safety follow-up visit date, whichever is later will be provided as shift tables.

#### 10.6.5 **Electrocardiogram**

ECG data are collected at screening. The investigator assessment of clinical significance categorized as normal, abnormal but not clinically significant, and abnormal clinically significant will be summarized. The number of subjects with corrected QT interval (QTc) greater than 480 msec will also be provided. A listing of subjects with abnormal and clinically significant baseline ECG results or QTc > 480 msec will be provided.

### 10.7 **Analyses of Efficacy Endpoints**

#### 10.7.1 **Definitions**

Study treatment response will be assessed according to response criteria of standardized tumor response and disease progression for MM ([Rajkumar 2011] and [Blade 1998]) including stringent complete response (sCR), complete response (CR), very good partial response (VGPR), partial response (PR), minimal response (MR), stable disease (SD), and disease progression. Overall response data will be summarized as follows:

- Overall Response Rate

ORR is defined as the proportion of subjects who achieve a sCR, CR, VGPR, or PR.

- Clinical Benefit Rate

Clinical benefit rate (CBR) is defined as the proportion of subjects who achieve a sCR, CR, VGPR, PR, or MR.

- Disease Control Rate

Disease control rate (DCR) is defined as the proportion of subjects who achieve a sCR, CR, VGPR, PR, MR, or SD.

- Duration of Response (DOR)

DOR is defined as the interval from the first documentation of sCR, CR, VGPR or PR to the first documentation of definitive disease progression or death from any cause. Data from surviving, non-progressing subjects will be censored at the earliest of the time of initiation of anticancer treatment other than the study treatment or the last time that lack of definitive MM progression was objectively documented. Data from subjects who have

MM progression or die after  $\geq 2$  consecutive missing tumor assessments will be censored at the last time before the missing assessments that lack of MM progression was objectively documented. The censoring rules for analyses of DOR are summarized in [Appendix 14.3](#).

- Progression-free Survival (PFS)

PFS is defined as the interval between the date of randomization to any study cohort and the first documentation of objective MM disease progression or death from any cause. Data from surviving, non-progressing subjects will be censored at the earliest of the time of initiation of anticancer treatment other than the study treatment or the last time that lack of MM progression was objectively documented. Subjects who have MM progression or die after  $\geq 2$  consecutive missing tumor assessments will be censored at the last time that lack of MM progression was objectively documented before the missing assessments. The censoring rules for analyses of PFS are summarized in [Appendix 14.3](#).

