## **3. STUDY OVERVIEW**

### **3.1 Study Design**

This study is a multicenter, open-label, randomized, parallel-group study to be conducted at approximately 20 sites in 2 countries (United Kingdom and United States). Forty subjects are planned to be randomized 1:1 into the following 2 cohorts to receive acalabrutinib, with or without dexamethasone:

- Cohort 1 (acalabrutinib monotherapy): acalabrutinib 100 mg bid continuously
- Cohort 2 (acalabrutinib + dexamethasone): acalabrutinib 100 mg bid continuously and 40 mg dexamethasone once weekly

Due to limited evidence of efficacy of acalabrutinib monotherapy in R/R MM subjects in this study, in a memo dated March 15, 2016 to all study sites, the enrollment was discontinued immediately and subjects who were randomized to receive acalabrutinib monotherapy were permitted to crossover to receive acalabrutinib + dexamethasone treatment.

One cycle is defined as a 28-day study treatment period. Treatment may be continued until disease progression (PD) or an unacceptable drug-related toxicity occurs. All subjects who discontinue study drug will have a safety follow-up visit 30 ( $\pm 7$ ) days after the last dose of study drug unless they have started another cancer therapy within that timeframe.

All subjects will have hematology, serum chemistry, and urinalysis safety panels done at screening. Once dosing commences (Day 1), all subjects will be evaluated for safety, including serum chemistry, and hematology, once weekly for the first 4 weeks, every 2 weeks in Cycle 2 and monthly thereafter. PK/PD testing will be done in Cycle 1 and Cycle 2. The end of trial is defined as the point when the last subject on the study exits the study for any reason.

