## **6.2 Treatment Cohorts**

Subjects are randomized with the ratio of 1:1 into 2 treatment cohorts to receive acalabrutinib, with or without dexamethasone:

- Cohort 1 (acalabrutinib monotherapy): acalabrutinib 100 mg bid continuously
- Cohort 2 (acalabrutinib + dexamethasone): acalabrutinib 100 mg bid continuously and 40 mg dexamethasone once weekly

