### 10.6 Analyses of Safety Endpoints

Safety analyses will be performed on All-treated population by treatment cohort.

Analyses of adverse events (AEs) will be performed on treatment-emergent AE (TEAE) data, unless otherwise specified. TEAEs are defined as those events with onset or

worsen date on or after the date of first dose of acalabrutinib, through the treatment phase to last dose of acalabrutinib, and within 30 days following the last dose of acalabrutinib, whichever is later. Common Terminology Criteria for Adverse Events (CTCAE) Version 4.03 or higher is used for AE grading.

Treatment-emergent AEs will be summarized in 3 groups: (1) acalabrutinib monotherapy, (2) acalabrutinib + dexamethasone, and (3) crossover from monotherapy to acalabrutinib + dexamethasone therapy. By this grouping method, AEs among subjects assigned to acalabrutinib monotherapy will be reported in group 1 when AEs occurred before crossover, and AEs occurred on/after crossover will be reported in group 3. Treatment-emergent AEs occurred on or after crossover will be summarized in the crossover group. Treatment-emergent AEs occurred before crossover will be summarized in the monotherapy group. All AE terms will be coded by Medical Dictionary for Regulatory Activities (MedDRA) Version 19.1 and will be presented by system organ class (SOC) and preferred term (PT). Treatment-emergent AEs will be summarized by SOC and PT and by CTCAE toxicity grade. The drug-related AEs, serious adverse events (SAEs) and drug-related SAEs, AEs leading to treatment discontinuation, dose delay and dose modification will be summarized by PT by CTCAE toxicity grade.

Death will be reported in a listing and summarized. A table will be provided for grade 5 AE and the relationship with any study drug.

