#### 10.7.2 Analysis Methods

The analysis of ORR, CBR, DCR, and PFS will be conducted on the All-treated Population. The analysis of DOR will be conducted on the subset of the All-treated Population who achieve sCR, CR, VGPR or PR as their best overall response.

ORR, CBR, DCR will be calculated and the corresponding 95% two-sided confidence intervals will be derived. DOR and PFS will be estimated using the Kaplan-Meier (KM) method. KM estimates with 95% CIs will be calculated for event time quartiles, including median. In addition, listings for DOR and PFS will be provided, including the reason for censoring.

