### 14.3 Censoring Rules for Duration of Response and Progression-Free Survival

Situation	Outcome	Event Description or Censoring Reason	Last Analysis Date
Documented disease progression before initiation of new anticancer therapy or on/before data cutoff date, whichever occurred first, also no more than 1 missing tumor assessments before documented disease progression	Event	Progressive Disease	Earliest date of documented disease progression
Death before initiation of new anticancer therapy or on/before data cutoff date, whichever occurred first	Event	Death	Date of Death
New anticancer therapy Initiated before data cutoff date and before documented disease progression or death	Censored	New anti-cancer therapy	Date of last adequate tumor assessment prior to initiation of new anticancer therapy
New anti-cancer therapy before data cutoff date for subjects without documented disease progression or death	Censored	New anti-cancer therapy	Date of last adequate tumor assessment prior to initiation of new anticancer therapy
No documented disease progression, initiation of new anticancer therapy or death on/before data cutoff date	Censored	Data cutoff	Date of last adequate tumor assessment on or before data cutoff date
No post-baseline adequate disease assessments	Censored	No post-baseline adequate disease assessments	Date of first dose of study drug

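### SAP 10.7 sets no crossover limit on Cohort 1 ORR and CBR, so a response first reached after dexamethasone was added can count in the monotherapy rate

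*SAP*

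**What the plan says.** **Response definitions.** SAP 10.7.1 states: "ORR is defined as the proportion of subjects who achieve a sCR, CR, VGPR, or PR". CBR is the same with MR added, and DCR adds SD. SAP 10.7.2 adds the analysis set, "The analysis of ORR, CBR, DCR, and PFS will be conducted on the All-treated Population", and 95% two-sided intervals. It limits DOR to subjects who "achieve sCR, CR, VGPR or PR as their best overall response", without saying when best response stops being counted.

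**Cohort label.** SAP 6.2 has "Cohort 1 (acalabrutinib monotherapy): acalabrutinib 100 mg bid continuously".

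**Routes to added dexamethasone.** Protocol 3.5.5.1 allows it for Cohort 1 subjects who have not reached MR after 2 cycles. SAP 3.1 summarizes a March 2016 memo under which "subjects who were randomized to receive acalabrutinib monotherapy were permitted to crossover to receive acalabrutinib + dexamethasone treatment", with no progression condition given. Protocol 3.1 also allows it on documented progression.

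**Adverse events.** SAP 10.6 splits at crossover: "AEs among subjects assigned to acalabrutinib monotherapy will be reported in group 1 when AEs occurred before crossover". Later events go to a third, crossover group.

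**New therapy.** For DOR and PFS, surviving subjects without progression are "censored at the earliest of the time of initiation of anticancer treatment other than the study treatment" or the last documented absence of progression. SAP 14.3 has a row for "New anticancer therapy Initiated before data cutoff date and before documented disease progression or death". It does not say whether added dexamethasone is such a therapy.

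**The concern.** Cohort 1 is described as monotherapy, and Protocol 5.2 says the sample size was chosen to judge each regimen's activity on its own. The Summary of Amendment 1 gives evaluation of single-agent activity as the reason for the 2-cycle wait. The 15% benchmark is the rate the documents associate with dexamethasone alone. A response that first appears after dexamethasone was added cannot be read as acalabrutinib acting alone against that benchmark.

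The SAP deals with this for adverse events and not for response. At stake is what the reported Cohort 1 ORR and CBR mean, and that matters more because SAP 11 says very few subjects responded.

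**Working it through.** **1. The plan's own figures.** Inputs from SAP 3.2: n = 19, null ORR 15%, alternative 40%, one-sided 0.025, exact binomial. The smallest qualifying cut-off is 7 of 19:
- P(X ≥ 6 | 0.15) = 0.0537, too large.
- P(X ≥ 7 | 0.15) = 0.0163.
- Power = P(X ≥ 7 | 0.40) = 0.692, matching the stated 69%.
- The 18.6% lower bound is reproduced by the exact (Clopper-Pearson) formula with x = 0.40 × 19 = 7.6, which gives 0.1864.

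No stated number is wrong. The gap is in the definitions.

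**2. Does any existing rule exclude a response after added dexamethasone?**
- SAP 10.7.1 censoring covers DOR and PFS only, and only treatment other than study treatment. Protocol 3.2.1 names dexamethasone as study drug, and SAP 10.5.3 treats it as one in the exposure analysis.
- SAP 14.3 covers DOR and PFS only.
- Protocol Table 4-2, footnote a, closes the response window when a new therapy follows study therapy. Dexamethasone added within the study does not meet that.
- Protocol 5.1 asks for analyses by dosing regimen, which fits either the assigned or the received regimen.

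None of these excludes a PR or MR first reached after a crossover without progression.

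**3. Which endpoints are affected.** ORR (PR or better) and CBR (MR or better) are. DCR hardly changes on the 2-cycle route, because a subject with SD already counts. For crossover after progression the position is unclear: SAP 10.7.2 does not say whether best response stops at first progression, and footnote a rules out several response categories when there is known progression in bone or a new bone lesion.

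**4. Size per response.** The documents give no Cohort 1 count. The plan was 20 per cohort and enrollment stopped early, so n = 20 and n = 15 are assumptions. Each added response is worth 100/n points: 100/20 = 5.0 and 100/15 = 6.7. Exact 95% limits are Beta(0.025; x, n − x + 1) and Beta(0.975; x + 1, n − x):

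| Responses | n = 15 | n = 20 |
|---|---|---|
| 0 | 0% (0–21.8) | 0% (0–16.8) |
| 1 | 6.7% (0.2–31.9) | 5.0% (0.1–24.9) |
| 2 | 13.3% (1.7–40.5) | 10.0% (1.2–31.7) |

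Counted from zero, one or two such responses leave the point estimate below 15%. The starting count matters: with one genuine earlier response, two more at n = 15 would give 3/15 = 20%.

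**5. Length of the pre-dexamethasone window.** As extracted, Protocol Appendix 5 places tumor assessments on Day 28 of each cycle, so a subject crossing over after 2 cycles has at most 2 scheduled assessments first. On the 8- to 12-week interval in Protocol 3.1 it is at most 1. For a subject followed through Cycle 12, disease markers fall at the end of Cycles 1 to 4 (4 times) and then every 2 months over Cycles 5 to 12 (about 4), so about 8 end-of-cycle assessments rest on markers.

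**The case against.** The strongest reply is that counting by randomized cohort is legitimate. Protocol 5.3 assigns efficacy to the ITT population, SAP 6.2 defines the cohorts by randomization, and PFS starts at randomization. The resulting rate describes a real strategy: start acalabrutinib and add dexamethasone if needed. This stands, and it is why that rate should be kept. But the SAP does not state the choice, and the rate is not a single-agent estimate.

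The second reply is that little turns on it. SAP 5 says no formal hypothesis is tested, and enrollment had already stopped for limited monotherapy efficacy. This also stands. A reader might infer that one misattributed response would change how Cohort 1 reads. The table does not support that: from zero, one response leaves the estimate at 5.0% or 6.7%, with limits reaching below 15% and not reaching 40%.

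Third, the memo is known only through the SAP's summary, so whether it allowed crossover without progression cannot be confirmed. The 2-cycle route in Protocol 3.5.5.1 is enough by itself.

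Fourth, a cut-off at added dexamethasone does not fully isolate single-agent activity, because the note to exclusion criterion 9 permits on-study systemic corticosteroids for myeloma. That is correct, and the listing below should show such use.

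Fifth, the DOR listing and the dexamethasone exposure data would let a reader trace some PRs. They would not cover MR, and they do not define the reported rate.

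**Conclusion.** The concern holds as a gap in the ORR and CBR definitions that should be fixed. Applied literally and by randomized cohort, SAP 10.7 lets a PR or MR first reached after added dexamethasone count as a Cohort 1 monotherapy response, while SAP 10.6 separates adverse events at the same point. The size is 5.0 to 6.7 points per such response, at assumed Cohort 1 sizes of 20 and 15. The effect is on a descriptive estimate; no test, error rate or stopping decision is affected.

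Two stronger readings are not supported. One is that the Cohort 1 rate is inflated: that needs a subject who crossed over and then responded, and the documents report none. The other is a stated chance of misattribution: that needs the number of crossovers without progression and their later response rate, and the documents give neither. Misattribution is possible; its likelihood is unknown.

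**What to change.** In SAP 10.7:
- Report Cohort 1 ORR and CBR as randomized and, beside that, from assessments before the first added dexamethasone. Keep all treated Cohort 1 subjects in both denominators.
- Summarize responses after crossover separately, parallel to the crossover group for adverse events.
- State how a response first seen before dexamethasone and confirmed after it is counted. Footnote a of Table 4-2 requires two consecutive assessments for PR or better.
- List responders with response date, crossover date and any other systemic corticosteroid given for myeloma.

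In SAP 14.3, state whether added dexamethasone counts as new anticancer therapy.

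The cost is a few sentences, a few table rows and one listing. Protocol 3.5.5.1 already requires regimen changes to be recorded on the eCRF. The main drawback is the shorter window: the pre-dexamethasone rate rests on at most 2 scheduled assessments for a subject crossing over after 2 cycles, fewer than a Cohort 2 subject who stays on treatment would have, and it may miss late single-agent responses. Neither rate should therefore be shown without the other.
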